**Rhythm Experience and Africana Culture Trial
(REACT)
NCT Number: NCT03771716**

Approved Protocol

Last Updated: August 29th, 2023

1.0 **SUMMARY:**

African Americans are almost two times more likely than whites (i.e., Caucasians) to experience Alzheimer's disease or other forms of dementia (1). Higher prevalence translates to 45% higher Medicare costs for African Americans compared to whites (2). A critical public health question emerges from these statistics that we intend to address in this study: Is there an effective method for reducing or eliminating the race disparities in cognitive and brain health?

Fortunately, physical activity (PA) interventions may be effective at improving neurocognitive function and reducing risk for dementia. Despite these promising results, prior PA interventions have had few African Americans making it difficult to stratify results by race to determine whether African Americans respond to PA in a similar manner and magnitude as whites. In addition, the terms 'physical activity' and 'exercise' are often considered unpleasant, painful, and fatiguing, which can negatively influence interest, enrollment, and long-term adherence to PA interventions.

Here, we propose an innovative and culturally sensitive method of increasing PA in older (60-80 yrs.) African Americans. We will conduct a ***randomized intervention*** where 180 older African Americans are assigned to either a moderate intensity ***African Dance*** group 3 days per week (N=90) or to an ***Africana Culture*** group 3 days per week (N=90) for 6-months. Both before and at the completion of the intervention, we will collect a comprehensive neuropsychological battery, physiological health metrics, and MRI metrics of brain health and function to identify biological pathways by which PA influences neurocognitive health in an African American population.

We have assembled a highly creative, productive, and interdisciplinary team with a long history of collaboration and experience conducting exercise interventions in older adults to test the following aims:

Aim 1. Examine whether a 6-month African Dance intervention improves cognitive performance compared to the culture control group. H1: The dance group will show cognitive improvements in a domain-specific fashion such that executive and memory functions will be enhanced more than other cognitive domains.

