Aim 3 proposes to explore physiological and socioemotional mechanisms of the dance intervention. We plan to explore our hypotheses using several different approaches including simple mediational models applying the change score method and will estimate whether the dance intervention (predictor) on *changes* in cognitive function outcomes are mediated through *changes* in the suspected mediators. Goodness-of-fit will be assessed through standard summary indices (e.g., RMSEA, CFI) and model assessment via residual analyses will be performed. Total, indirect and direct effects will be estimated. Additionally, we will explore mediation applying the half-longitudinal approach proposed by Cole and Maxwell as well as an autoregressive mediational approach. Finally, we will explore recent advancements in repeated measures mediation analyses developed by Preacher and Hayes. Depending on the results from simple mediational modeling, we may also combine mediators into a multiple mediator model to develop a more comprehensive picture of these pathways.

1.3.2 Power Analyses. Our planned sample size of 180, with randomization of 90 participants in each group, is based on effect sizes from preliminary data. Even when accounting for attrition and retention of ~70% of participants (65 in each group), we are sufficiently powered to detect effects in cognitive and brain outcomes and to test for mediation.

1.3.3 Cognitive performance. Our prior PA interventions have found moderate sized effects on cognitive function after 6-months with a Cohen’s d ranging from 0.40 to 0.80 depending on the outcome (23). In our analysis of the pilot data from the African Dance intervention with only 19 participants (9 in the Dance group) we estimate similar or greater effect sizes of ~.70. If we estimate an effect of 0.70, 65 participants per group after attrition will provide us with >91% power to examine our primary hypotheses.

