After the completion of the measures and sessions described above the participants will be randomly assigned to one of two groups: (a) The Dance condition will consist of approximately 180 minutes per week of moderate intensity African Dance, or (b) an Africana Culture control condition that will consist of 180 minutes per week of mixed-programming related to African Culture, including art projects, cooking, and films. We will use a computer randomization protocol that will incorporate a verification that all session visits have been completed and data entered into the database. We will use a stratified permuted block randomization algorithm with equal allocation to one of the two groups. The use of this strategy will ensure treatment balance on the two factors of age at study entry ($=<70, >70$) and gender. Once randomized, an assigned staff member will contact the subject via phone with the group information. On this contact, the staff

member will give information such as date, day, time, and location of the subject's first intervention session.

1.10 EXERCISE INTERVENTION GROUPS:

1.10.1 African Dance Group. Participants in the Dance condition will begin by dancing at reduced intensity during the first week of the program and will gradually increase their dancing intensity each subsequent week until they reach 40-60% of their heart rate reserve for all of the dance class. All dance sessions start and end with 5-10 minutes of active stretching for the purpose of warming up and cooling down. As the participants will be low active at baseline, the prescribed intensity will be 50–65% of the maximum heart rate reserve for weeks one to four and 65–80% for the remainder of the program. Participants will be fitted with a Polar Bluetooth Smart heart rate sensor around their chest and be encouraged to dance within their target heart rate zone by fitness staff. Continuous heart rate readings of all participants will be displayed in real-time via the Polar Team app on an iPad or other tablet. Certified exercise instructors will closely monitor attendance, intensity, frequency, and safety. Dance sessions will occur three days/week at one of two study sites for the duration of the intervention.

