1.11 ANALYSIS PLAN

Our analysis plan has proposed an intent-to-treat analysis where all participants, regardless of whether they complete all sessions, will be invited to return for follow-up assessments. However, there will likely be some participants that refuse to return for follow-up assessments. “Lost to follow up” will be defined here as missing data that is contributing to the primary outcomes (executive functioning and hippocampal volume). The reason will be recorded (i.e., missed visit due to traveling, illness). These criteria and documentation will also be applied for any discontinued subjects with the reasons for discontinuation being recorded (i.e., moving out of state).

We propose to use all available data in the planned analysis for testing our primary outcomes. We will assess the missingness of data consistent with the assumptions of the modeling approach described above. That is, we will examine the randomness of missing data and examine if the data is missing completely at random (MCAR) or missing at random (MAR). Parameters of the GLMM will be estimated using the maximum likelihood estimation or restricted maximum likelihood methods that are known to produce consistent and efficient estimates under MAR.

Imaging data analysis. We will first analyze each imaging outcome (e.g., volume) separately from every other imaging outcome (e.g., fMRI). But, once voxel-wise associations related to the intervention are established, we could test, using hierarchical regression, the relative significance of each imaging measure to explain improvements in cognitive function with the intervention.

1.12 PARTICIPANT SAFETY:

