We will describe differences in baseline characteristics between participants with complete versus incomplete follow-up to assess any bias (e.g., age) in those who do not return for follow-up. However, according to ITT analyses, all participants including those that do not complete the intervention will be analyzed as part of the trial. Using hierarchical regression models, we will be able to explore whether changes in any cognitive or neuroimaging metric (e.g., white matter integrity) varies as a function of improvements in PA or fitness independently of assigned group. We also appreciate that there will be significant individual variability in factors such as body mass, blood pressure, fitness level, or SES. Instead of modeling this variation as ‘noise’ we plan to take advantage of the variability to further explore, independently of group assignment, the associations between cognitive and brain imaging metrics and initial levels and individual change trajectories. Main effects and interaction terms will be modeled in these regression analyses and time-dependent changes will be explored and illustrated by scatter plots. These analyses will be useful for generating future hypotheses and questions.

Power Analyses: Our proposed sample size of 180, with randomization of 90 participants in each group, is based on effect sizes from preliminary data. Even when accounting for attrition and retention of ~70% of participants (65 in each group), we are sufficiently powered to detect effects in cognitive and brain outcomes and to test for mediation.

Cognitive performance: Our prior PA interventions have found moderate sized effects on cognitive function after 6-months with a Cohen’s d ranging from 0.40 to 0.80 depending on the outcome. In our analysis of the pilot data from the African Dance intervention with only 19 participants (9 in the Dance group) we estimate similar or greater effect sizes of ~.70. If we estimate an effect of 0.70, 65 participants per group after attrition will provide us with >91% power to examine our primary hypotheses.

Brain volumetrics: Our prior 6-12 month PA interventions have used between 30 and

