60 subjects per group with Cohen's d ranging between 0.40 and 0.50 using similar analysis approaches. Cross-sectional research has reported significant effects of PA on brain volume with only 32 subjects and effect sizes between 0.50 – 0.60. Preliminary data on 37 African Americans from one of our prior studies suggest that cross-sectional differences between African Americans engaging in PA compared to those not engaging in PA are larger than for whites (Cohen's d = 1.83). These studies argue for a moderate-to-large effect of PA on brain volume depending on the sample, the measure of PA and fitness, and the brain metric used. If we estimate a conservative effect size of 0.50, 65 participants per group will be sufficient to detect differences in brain volume at 81% power.

Diffusion tensor imaging: Changes in white matter have been detected in PA interventions in as little as 6-months with only 50 subjects. In a 12-month PA intervention, we found increased FA with only 35 subjects in each group with an estimated effect size of 0.70. Based on an estimated effect size of 0.75, we should have >85% power with 65 participants per group to test our main hypotheses as well as enough power for exploratory analyses.

Task-evoked activity: Task-evoked brain imaging studies of PA have found statistically significant effects with 30 - 50 subjects per group with effect sizes ranging between 1.0 and 1.3 depending on the region examined and the task employed. Cross-sectional studies of fitness on brain activity report even larger effects up to 1.70. These patterns indicate a large effect size of PA on brain function, so 65 participants per group will provide us with substantial power to test our main aims and hypotheses.

Connectivity: With only 65 people, we have shown that a PA intervention is effective at enhancing functional connectivity in prefrontal-inhibitory networks. The difference between the groups for prefrontal cortex connectivity was .15 with a standard deviation of .10 suggesting an effect size of 1.5 (Cohen's d). Therefore, similar to the effect sizes and power for the other measures, 65 participants per group should be sufficient for detecting changes as a function of the intervention with >85% power.

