Given the continued challenges of navigating the COVID-19 pandemic, we requested to modify our recruitment/randomization accrual and targeted sample size for the study titled "Rhythm Experience and Africana Culture Trial (REACT II)" on August 29th, 2023. We have determined that we will have sufficient statistical power to test our primary aims with a reduction in the targeted sample size from 180 to 150.

The recommended changes were approved by the meeting of the Data Safety and Monitoring Board on August 29, 2023.

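### After the cut from 180 to 150, the power text still assumes 65 completers per arm; at the plan's own retention of about 70-72%, brain-volume power is about 71-73%, not 81%

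*Combined protocol and SAP*

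**What the plan says.** The current sample-size statement is the note at the end of the SAP, dated August 29, 2023. It cites the pandemic, reports approval by the Data Safety and Monitoring Board, and says there will be "sufficient statistical power to test our primary aims with a reduction in the targeted sample size from 180 to 150". No calculation accompanies it.

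The rest of the document still describes the larger trial:

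- Section 1.0: "180 older African Americans are assigned to either a moderate intensity" dance group or the culture group, 90 in each.
- Section 1.3.2: "Our planned sample size of 180, with randomization of 90 participants in each group, is based on effect sizes from preliminary data".
- Section 1.3.2 and the SAP, Power Analyses: "Even when accounting for attrition and retention of ~70% of participants (65 in each group"), with power described as adequate for cognition, brain outcomes and mediation.
- Section 1.3.4 and the SAP, Brain volumetrics: at an effect size of 0.50, which the plan calls conservative, "65 participants per group will be sufficient to detect differences in brain volume at 81% power". The same paragraph gives the sponsor's earlier 6-12 month interventions as Cohen's "d ranging between 0.40 and 0.50 using similar analysis approaches".

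Two further passages matter. Section 1.9 specifies a "stratified permuted block randomization algorithm with equal allocation to one of the two groups". Section 1.11, in defining loss to follow-up, names the "primary outcomes (executive functioning and hippocampal volume").

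**The concern.** The sponsor justifies the reduction by power, but every power figure in the document belongs to the design being replaced. The brain-volume figure deserves most attention because it had almost no margin: 81% at the plan's chosen effect. A one-sixth cut in randomised participants (30 of 180), with retention unchanged, must take it below 80%.

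Brain volume is also not a side measure, since hippocampal volume is one of the two named primary outcomes. A reader of the current text would credit that comparison with 81% power. If the true figure is nearer 72%, the chance of missing an effect of the assumed size rises from about 19% to 27-29%, and a null hippocampal result would be less informative than the document suggests.

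**Working it through.** **Inputs**

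- Reduced target: 150 (SAP closing note). Equal allocation (1.9) gives 150/2 = 75 per arm.
- Retention: about 70% as stated, or 65/90 = 72.2% as implied by the plan's own numbers (1.3.2; SAP, Power Analyses).
- Brain-volume effect: d = 0.50 (1.3.4; SAP, Brain volumetrics).
- Two-tailed tests (1.3.1; SAP). The alpha level is not stated; 0.05 is assumed.

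**Method.** Two-sample t-test with n per arm, df = 2n − 2 and noncentrality d·√(n/2). Power is the probability that |T| exceeds the two-sided 5% critical value.

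**Step 1: reproduce the plan's figure.** For n = 65 and d = 0.50, the noncentrality is 0.50 × √32.5 = 2.85 and the critical value is 1.979. Power is 80.8% (81.3% by the normal approximation), which matches the stated 81%. Other settings do not match: one-sided 0.05 gives 88.6% (normal approximation) and two-sided 0.025 gives 71.9%.

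**Step 2: completers under the reduced target.** 75 × 0.70 = 52.5, and 75 × 65/90 = 54.2, so 52-54 per arm.

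**Step 3: brain-volume power at d = 0.50**

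| Completers per arm | Retention of 75 | Power |
|---|---|---|
| 52 | 69% | 71.4% |
| 53 | 71% | 72.2% |
| 54 | 72% | 73.1% |
| 60 | 80% | 77.5% |
| 64 | 85% | 80.1% |
| 65 | 87% | 80.8% |

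The normal approximation is less than one point higher (72.2-73.8% at 52-54).

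**Step 4: retention needed.** 80% power at d = 0.50 takes 63.8, so 64 per arm: 64/75 = 85.3%. Keeping 65 per arm takes 65/75 = 86.7%.

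**Step 5: effect detectable with 80% power.** d = 0.495 at 65 per arm, 0.544 at 54 and 0.555 at 52. The last two lie above the 0.40-0.50 range that the plan reports from its own earlier interventions. At d = 0.40, power was already 61.9% with 65 per arm and becomes 52.4-54.0% with 52-54.

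**Step 6: the other power claims at 52-54 per arm, same test**

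- Cognition, d = 0.70: 94.2-95.0% (stated as above 91%).
- DTI, d = 0.75: 96.6-97.1% (stated as above 85%).
- Task-evoked activity and connectivity, d of 1.0 or more: at least 99.9%.

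**The case against.** The strongest reply is that the 81% is attached to 65 per group and is correct for 65; nowhere does the document claim 81% for a trial of 150. That is true. What fails is the combination of an unquantified assurance of sufficient power and power text that was never updated, so the only figure a reader can find does not describe the current design.

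Second, retention may be better than the planning allowance. Everyone is invited back whether or not they finish the classes, and by August 2023 the sponsor may have known its actual retention. This is possible, but no such figure is given, and even 80% retention yields only 77.5%.

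Third, the planned mixed model uses baseline and all available data and could be more powerful than a t-test on completers. The plan gives no baseline to follow-up correlation with which to quantify this, and its own 81% matches the simple two-group test.

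Fourth, the d = 0.50 is for brain volume in general, and hippocampal volume is called primary only inside a definition of loss to follow-up. No separate hippocampal power is stated, so applying the brain-volume figure is an inference, although the plan offers no other figure for that outcome. Nor do the documents set 80% as a formal target; it serves here only as a reference point beside the plan's 81%.

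Finally, the reassurance about the other outcomes depends on alpha 0.05. At 65 per arm that level gives 97.7% for cognition, well above the stated bound of 91%. Two-sided alpha 0.01 would give 91.35% at 65 and only 82.5-84.2% at 52-54. The same 0.01 level gives 59.4% for brain volume at 65, so it cannot be the level behind the 81%. This is a further reason to state alpha. Power for mediation carries no figure in the plan and was not checked.

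**Conclusion.** The concern holds. On the plan's own effect size and retention, and the test that reproduces its 81%, the reduced design has about 71-73% power for brain volume: a loss of about 8 to 9 points, with the effect detectable at 80% power moving from about 0.50 to 0.54-0.55. The statement of sufficient power therefore cannot be reproduced for one of the two named primary outcomes. The result rests on two-sided alpha 0.05, 75 per arm from equal allocation, retention of 70-72%, and the general brain-volume effect being applied to the hippocampus. It does not show that the trial is underpowered overall or that the reduction was wrong: at the same alpha, the cognitive and DTI claims still hold at 52-54 per arm. It should be fixed.

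**What to change.** Restate the power text in 1.3.2-1.3.7 and the SAP for 150 randomised, 75 per arm, giving the alpha, retention and completers used. Suitable wording: *With 75 randomised per arm and about 70-72% retention, 52-54 per arm are expected at follow-up. At two-sided alpha 0.05 this gives about 71-73% power for brain volume at d = 0.50, and 80% power for d of about 0.55.*

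If observed retention supports a higher figure, report it instead: about 64 of 75 per arm for 80% power, 65 of 75 for 81%.

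Limit the claim of sufficient power to the outcomes for which it holds. Because the closing note records a dated decision, a dated addendum to it would serve. Reconcile 180/90 with 150/75 in 1.0, 1.3.2 and the SAP.

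The cost is wording in the protocol, the SAP and the note, and a less favourable stated power for brain volume. Enrolment, endpoints and analysis do not change. Since the board approved the reduction, it would be sensible to send it the restated figures.
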